1.5.2 Phase I clinical pharmacodynamic (PD) observation of apatinib

From May 2007 to December 2008, a phase I clinical study of apatinib was conducted at Fudan University Shanghai Cancer Center, including 3 studies, i.e., a tolerability study, a pharmacokinetic study, and a phase I supplement clinical study. This study enrolled a total of 81 subjects with advanced solid tumors who were refractory to standard treatment or had no effective standard treatment. Nine of the subjects were not evaluated, and 3 others were only administered with a low dose of 250 mg/day. A total of 69 subjects received apatinib treatment at doses of 500–1000 mg/day (only 3 subjects received 1000 mg/day), and a total of 56 patients were evaluated. Refer to [Table 2](#) for a summary of tumor types of the 69 subjects and efficacy in the 56 evaluable subjects:

Table 2. Efficacy of apatinib in the treatment of different solid tumors

	Gastric Cancer	Colorectal Cancer	Lung Cancer	Breast Cancer	Nasopharyngeal Cancer	Renal Carcinoma	Esophageal Cancer	Hepatocellular Carcinoma	Small Intestinal Stromal Tumor	Neurilemmoma Malignant of Left Iliac Fossa
Not Evaluable	1	7	1	1	1	0	1	1	0	0
CR	0	0	0	0	0	0	0	0	0	0
PR	2	2	0	0	0	1	0	0	1	0
SD	5	15	3	4	1	0	4	1	0	0
PD	1	7	1	2	0	0	0	0	0	1
Death Without Evaluation	3	1	0	0	0	0	0	0	0	0
Objective Response Rate	18.1%	8%	0	0	0	100%	0	0	100%	0
Disease Control Rate	63.6%	68%	75%	66.7%	100%	100%	100%	100%	100%	0
Total	12	32	5	7	2	1	5	2	1	1

Result analysis:

A total of 69 subjects with various types of solid tumors were included in statistical analysis, and 13 were deemed unevaluable for efficacy. Of the 69 subjects included in the statistics, 16 subjects were given 500 mg, 37 subjects were given 750 mg, 13 subjects were given 850 mg, and 3 subjects were given 1000 mg.

Analysis of ORR showed that 1 evaluable case was found for each of renal carcinoma and small intestinal stromal tumor, with both achieving PR. 11 and 25 evaluable patients were included for the gastric cancer and colorectal cancer respectively, and higher response rates of 18.1% and 8%, respectively, were achieved.

Based on the analysis of DCR, 1 each of evaluable patient for nasopharyngeal cancer, HCC, and GIST were observed, and all had achieved SD. Due to the small sample size, the efficacy should be assessed with caution. There were 4, 4, and 6 evaluable patients for esophageal cancer, lung cancer, and breast cancer, respectively, with DCRs of 100%, 75%, and 66.7%.

1.5.3 Phase I clinical pharmacokinetic study of apatinib

The single-dose study involved oral administration at 3 dose levels of 500, 750 and 850 mg to subjects with cancer, including 7 male subjects and 5 female subjects in low-dose group, 6 male subjects and 3 female subjects in medium-dose group, and 6 male subjects and 6 female subjects in high-dose group. In this study, drugs were administered within 0.5 h after meals, and blood and urine samples were collected at multiple time points within 48 h. Results showed that M1 was a major metabolite of apatinib in humans, with $AUC_{M1}/AUC_{apatinib}$ of 1.15-5.06, as well as 48-h cumulative excretion in urine, $Cum.Ae_{M1}/Cum.Ae_{apatinib}$ of 24.5-353. $T_{1/2}$ values of apatinib and M1 were 8.93 ± 0.81 h and 12.5 ± 1.666 h, respectively. At the same dose level, large inter-individual variability was seen in apatinib and M1 exposure (AUC and C_{max}); significant gender difference was observed in the high-dose group ($P < 0.05$), in which, AUC in females was 1.96 times higher than that in males, and C_{max} was

3.57 times higher than that in males. The levels of apatinib and M1 exposure in male and female subjects were non-linearly but positively correlated to oral doses.

The food-effect study mainly compared the differences in absorption of a single oral dose of apatinib given at 1 h before meals and 0.5 h after meals. The concentrations of M1 were also examined. Blood and urine samples were collected at multiple time points within 48 h.

Results showed that there was no significant difference in T_{max} and C_{max} of apatinib in the blood of male and female subjects with respect to the order of eating and drug administration ($P > 0.05$). In addition, the AUC, $T_{1/2}$ and Cum.Ae of apatinib, as well as relevant pharmacokinetic parameters of M1 were not affected by the order of eating and drug administration ($P > 0.05$).

Due to the relatively long half-life of M1 ($T_{1/2}$: 12.9 ± 1.85 h), the repeated-dose trial mainly focused on M1 accumulation in vivo, and changes in apatinib ($T_{1/2}$: 9.24 ± 1.40 h) concentrations were observed concurrently during the trial. The drugs were administered once a day for 4 weeks during the trial, and blood and urine samples were collected at multiple time points within 24 h on Days 1, 14, and 28 after the start of the trial. Results showed that: Although M1 and apatinib had relatively long half-lives, no significant accumulations of M1 and apatinib were observed in subjects on D14 vs. D1 ($P > 0.05$). However, a significant increase in M1 exposure was noted in male subjects on D28 vs. D1 ($P < 0.05$). Apatinib: AUC (1d), AUC (14d), and AUC (28d) were 9260 ± 4308 , 7256 ± 4709 , and 21930 ± 20098 ng·h/mL, respectively; C_{max} (1d), C_{max} (14d), and C_{max} (28d) were 1285 ± 776 , 693 ± 430 , and 1602 ± 1755 ng/mL, respectively. M1: AUC (1d), AUC (14d), and AUC (28d) were 13846 ± 7061 , 10899 ± 6702 , and 39784 ± 21900 ng·h/mL, respectively; C_{max} (1d), C_{max} (D14d), and C_{max} (28d) were 1193 ± 673 , 908 ± 597 , and 1728 ± 1233 ng/mL, respectively. There was no significant accumulation of apatinib and M1 based on the cumulative levels of urinary and renal excretion ($P > 0.05$). Cum.Ae (1d), Cum.Ae (14d), and Cum.Ae (28d) of M1 were 30281 ± 8141 , 34537 ± 15867 , and 33466 ± 17737 μ g, respectively.

AEs in the placebo, 850 mg q.d., and 425 mg b.i.d. groups were reported by 36, 42, and 44 subjects, with incidences of 75%, 89.36%, and 95.65%, respectively; severe AEs (NCI CTC Grade III–IV) occurred in 18, 30, and 48 subjects, with incidences of 37.5%, 48.94%, and 73.91%, respectively. The incidence of AE was higher in both 850 mg q.d. and 425 mg b.i.d. groups as compared with the placebo group, and the incidence in the 425 mg b.i.d. group was higher than that in the 850 mg q.d. group.

1.5.6 Results of phase III clinical trial of apatinib in patients with gastric cancer

This is a randomized, double-blind, parallel-controlled, nation-wide multi-center phase III clinical trial to validate the efficacy and safety of apatinib in patients with advanced gastric cancer.

In this trial, 267 randomized patients who received at least one dose were included in FAS analysis, including 176 patients in the treatment group and 91 patients in the control group.

In the FAS, endpoint events were observed in 146 (82.95%) subjects in the treatment group and 78 (85.71%) subjects in the control group, with an incidence > 80% in both groups, indicating that the statistical model is reliable.

Analysis showed that as of 23 May, 2013, without taking the influence of crossover design into consideration, median OS (mOS) values were 6.5 and 4.7 months in the treatment and control groups, respectively. The mOS in the treatment group was 1.8 months longer than the control group, $P = 0.0149$. The HR of treatment group to control group was 0.709 and the 95% CI was (0.537, 0.937), with $P = 0.0156$. The above results demonstrated that apatinib provided significant survival benefits when compared with placebo.

All the 267 subjects in this trial were included in the SS for analysis. Results showed that:

The incidences of AEs in the treatment and control groups were 98.30% v.s 90.11%, $P = 0.0038$; the incidences of Grade \geq II AEs were 88.07% v.s 67.03%, $P = 0.0001$; the incidences of Grade III–IV AEs were 60.23% v.s 41.76%, $P = 0.0045$.

The incidence of ADRs in the treatment and control groups were 92.05% v.s 71.43%, $P = 0.0000$; the incidence of Grade \geq II ADRs were 80.68% v.s 45.05%; the incidences of Grade III–IV ADRs were 51.70% v.s 24.18%, $P = 0.0000$.

The incidence of SAEs in the treatment and control groups were 15.34% v.s 16.48%, $P = 0.8598$; the incidence of serious ADRs were 6.25% v.s 6.59%, $P = 1.0000$.

1.5.7 Results of phase II clinical trial of apatinib in patients with HCC

A randomized, open-label, multi-center phase II clinical trial evaluating apatinib mesylate tablets in advanced HCC was initiated in Jul. 2010 by the 81st Hospital of the Chinese People's Liberation Army and other sites.

The trial involved two treatment groups: 850 mg and 750 mg groups. Primary endpoint: TTP; secondary endpoints: OS, ORR, DCR, AFP, QoL, and safety.

Simon's two-stage design for the clinical study of anti-tumor drugs is used. Sample size is determined based on disease control rate (DCR). It was assumed that patients receiving the best supportive care for this indication could achieve DCR of 30%. Patients in the apatinib group achieved DCR of 50%, indicating that apatinib is superior to the best supportive care in terms of DCR. Based on the optimal design criteria, with $\alpha = 0.05$ and $\beta = 0.2$, and using

NCSS & PASS, 15 patients were enrolled in each group in the first stage. If 5 patients reach DCR, the sample size would be expanded to 46 patients. If 15 of the 46 patients reach DCR, subsequent studies could be carried out at this dose. Taking dropout factors into consideration, a total of 36 subjects were enrolled in the first stage, and sample size was expanded to 117 in the second stage, i.e., 81 subjects were enrolled (including 51 in the 850 mg group and 30 in the 750 mg group).

As of Jun. 2013, the results are as follows:

The phase II clinical trial of apatinib mesylate tablet in patients with advanced HCC had an actual enrollment of 121 subjects, including 70 in the 850 mg group and 51 in the 750 mg group.

Efficacy results showed that in the FAS (ITT population), mTTP values in the 850 mg and 750 mg groups were 4.2 and 3.3 months, and mOS values were 9.7 and 9.8 months, respectively. ORRs were 8.6% and 0.0%, and DCRs were 48.6% and 37.3%, respectively.

Table 4. Inter-group comparison of efficacy results (FAS)

Group	mTTP (month)	mOS (month)	ORR (%)	DCR (%)
850 mg	4.2	9.7	8.6	48.6
750 mg	3.3	9.8	0.0	37.3

Safety results showed that the incidences of AEs in the 850 mg and 750 mg groups were 98.6% and 94.1%, respectively; the incidences of severe AEs (NCI CTCAE Grade III–V) were 67.1% and 72.6%, respectively. The incidences of ADRs in the 850 mg and 750 mg groups were 95.7% and 90.2%, respectively; the incidences of severe ADRs (NCI CTCAE Grade III–V) were 58.6% and 58.8%, respectively. The incidences of SAEs were 18.6% and 23.5%, respectively; and the incidences of serious ADRs were 4.3% and 5.9%, respectively.

Table 5. Comparison of the incidences of AEs and ADRs between the two groups (SS)

	Group	Yes	No	Total	Incidence (%)	Inter-Group Comparison P
Adverse Events (n)	850 mg group	69	1	70	98.57	0.3090
	750 mg group	48	3	51	94.12	
Grade III–V Adverse Events (n)	850 mg group	47	23	70	67.14	0.5551
	750 mg group	37	14	51	72.55	
Adverse Drug Reactions (n)	850 mg group	67	3	70	95.71	0.2790
	750 mg group	46	5	51	90.20	
Grade III–V Adverse Drug Reactions (n)	850 mg group	41	29	70	58.57	1.0000
	750 mg group	30	21	51	58.82	

	Group	Yes	No	Total	Incidence (%)	Inter-Group Comparison P
Serious Adverse Events	850 mg group	13	57	70	18.57	0.5060
(n)	750 mg group	12	39	51	23.53	
Serious Adverse Drug Reactions	850 mg group	3	67	70	4.29	0.6960
(n)	750 mg group	3	48	51	5.88	

Common adverse events (incidence $\geq 10\%$) mainly included: transaminases increased, hypertension, proteinuria, hand-and-foot syndrome, etc., most of which were mild to moderate, and all were controllable. Refer to Table 6 for details:

Table 6. Common AEs (incidence $\geq 10\%$) in both groups

Adverse Events	Group	Total	Adverse Events n (%)	Grade III–V Adverse Events n (%)
Transaminases Increased	850 mg	70	44 (62.9)	8 (11.4)
	750 mg	51	25 (49.0)	7 (13.7)
Bilirubin Increased	850 mg	70	44 (62.9)	8 (11.4)
	750 mg	51	24 (47.1)	8 (15.7)
Hypertension	850 mg	70	36 (51.4)	3 (4.3)
	750 mg	51	25 (49.0)	7 (13.7)
Proteinuria	850 mg	70	33 (47.1)	1 (1.4)
	750 mg	51	24 (47.1)	2 (3.9)
Gamma-Glutamyltransferase Increased	850 mg	70	30 (42.9)	13 (18.6)
	750 mg	51	6 (31.4)	5 (9.8)
Hand-and-Foot Syndrome	850 mg	70	29 (41.4)	4 (5.7)
	750 mg	51	15 (29.4)	4 (7.8)
Platelet Count Decreased	850 mg	70	27 (38.6)	6 (8.6)
	750 mg	51	23 (45.1)	7 (13.7)
White Blood Cell Count Decreased	850 mg	70	21 (30.0)	3 (4.3)
	750 mg	51	17 (33.3)	2 (3.9)
Lactate Dehydrogenase Increased	850 mg	70	19 (27.1)	2 (2.9)
	750 mg	51	6 (11.8)	2 (3.9)
Neutrophil Count Decreased	850 mg	70	18 (25.7)	4 (5.7)
	750 mg	51	16 (31.4)	3 (5.9)
Abdominal Pain	850 mg	70	18 (25.7)	4 (5.7)
	750 mg	51	7 (13.7)	0 (0.0)
Asthenia	850 mg	70	17 (24.3)	3 (4.3)
	750 mg	51	9 (17.7)	2 (3.9)

The 850 mg and 750 mg groups had comparable efficacy. In terms of safety, the types and incidence of AEs and ADRs observed in both groups were also similar.

2 STUDY OBJECTIVES AND ENDPOINTS

2.1 Study Objectives

To observe and evaluate the efficacy and safety of apatinib mesylate tablet as second-line treatment in patients with advanced HCC.

2.2 Primary Endpoints

- Overall survival (OS)

Defined as the time from randomization to death from any cause.

2.3 Secondary Endpoints

- Progression free survival (PFS)

Defined as the time from randomization to the occurrence of progressive disease (PD) or death, whichever occurs first.

- 3-, 6-, and 12-month PFS rates

Defined as the proportions of evaluable patients without disease progression from the start of the trial to 3, 6, and 12 months.

- Time to progression (TTP)

Defined as the time from randomization to radiographic disease progression.

- Objective response rate (ORR)

Defined as the proportion of evaluable subjects who have a tumor response assessed by RESIST 1.1, including complete response (CR) and partial response (PR).

- Disease control rate (DCR)

Defined as the proportion of evaluable subjects who have disease control assessed by RESIST 1.1, including CR, PR and stable disease (SD) (≥ 4 weeks) .

Evaluable subjects are defined as all subjects who have received at least 2 cycles (8 weeks) of apatinib treatment and have received a tumor evaluation after 2 treatment cycles (8 weeks). If the efficacy reaches CR, PR or SD, the subject must be reexamined 4 weeks after the first evaluation.

- The percentage of evaluable patients with stable disease (SD) of ≥ 4 weeks (confirmed SD in particular)
- 6- and 12-month mortalities
- Quality of life score (EORTC QLQ-C30 and HCC-18);

- Drug safety: Vital signs, laboratory measurements, AEs, SAEs, treatment-related AEs and SAEs, and AEs of special interest (e.g., hypertension, proteinuria, and hand-and-foot syndrome [palmar-plantar erythrodysesthesia syndrome]); judged as per NCI-CTCAE V4.0.

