- (7) f: Echocardiography: Must be performed during the screening period. For clinically significant ECG abnormalities observed during the study period, an additional echocardiography examination is required.
- (8) g: ECG: The QTc interval must be indicated for 3 times, with about 5 min apart. ECG examination shall be carried out before drug administration during the screening period and then always after drug administration in each visit. For clinically significant ECG abnormalities, an additional echocardiography examination is required; if there are symptoms such as precordial pain and palpitations, the myocardial zymogram (creatinine kinase, lactate dehydrogenase) should be tested immediately. The examination should be carried out every two cycles after Cycle 3.
- (9) h: Quality of life score: Must be measured before the efficacy evaluation; and measured every two cycles after Cycle 3.
- (10) i: Imaging examination: Screening period: including CT or MRI of the chest and abdomen. Brain CT/MRI is required for clinically suspected metastases to the central nervous system. A bone scan is required for clinically suspected bone metastasis. Treatment period: The examination should be carried out in Cycles 2 and 3, and then every two cycles after Cycle 3.
- (11) i: Efficacy evaluation: The first efficacy evaluation is carried out at the end of Cycle 2; efficacy confirmation is carried out at 4 weeks after the first efficacy evaluation (i.e., at the end of Cycle 3). Afterwards, the efficacy evaluation is carried out every two cycles; For subjects who withdraw from the study due to unacceptable toxicity, the efficacy evaluation should be conducted upon withdrawal if the efficacy evaluation is not carried out within 4 weeks before withdrawal. Thereafter, the imaging examination is performed every 2 cycles until progressive disease.
- (12) Follow-up 1 (can be repeated for V101): The subjects who withdraw from the study due to unacceptable toxicity should be followed-up for tumor progression until the tumor progression is confirmed by imaging or the start of new anti-tumor treatment.
- (13) Follow-up 2 (can be repeated for V201): Survival follow-up, visit number from 201, 202, 203...

REGULATIONS FOR DOSE MODIFICATION

NCI Toxicity Grade	Regulations for Dose Modification	Regulations for Toxicity Recovery upon Re-Administration after Treatment Discontinuation	Regulations for Toxicity Recovery at the Beginning of Next Cycle

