### **6.2 Per-Protocol Set (PPS)**

The PPS is a subset of the FAS and is defined as all subjects who are in compliance with the protocol, have good compliance, have received at least 1 cycle of the study drug (except for those with clear medical evidence of PD), and have completed the eCRF.

The statistical analysis will be performed for the drug efficacy based on the FAS and PPS. Before database locking, the principal investigator, statistician, and sponsor determine the final PPS during the data review meeting.

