### **6.3 Safe Set (SS)**

The SS is defined as all randomized subjects who have received at least one dose of the investigational drug and have safety records after drug administration.

For the safety analysis, all subjects should be analyzed based on the group of actually received study drug.

In this trial, baseline data are analyzed based on the FAS; primary efficacy endpoints are analyzed based on FAS (primary) and PPS; data of laboratory tests and AEs/Treatment-related AEs are analyzed based on the SS. In addition, ORR, DCR, and the percentage of subjects with SD will also be analyzed among subjects with evaluable efficacy.

Subjects with evaluable efficacy are defined as all subjects who have received at least 2 cycles (8 weeks) of apatinib treatment and received a tumor evaluation after 2 treatment cycles (8 weeks). If the efficacy reaches CR or PR, it should be confirmed 4 weeks later.

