### 7.3.2 Analysis of secondary efficacy endpoints

- Secondary efficacy endpoints of PFS and TTP are summarized using descriptive statistics based on FAS and PPS according to the above general principles and analyzed using similar methods as those for primary efficacy endpoint.
- Based on FAS and PPS, the 3-, 6-, and 12-month PFS rates, the Kaplan-Meier method was used to estimate rates and corresponding 95% CIs of the two groups are calculated using the log-log transformation according to the normal approximation with back transformation to CIs on the untransformed scale.
- The secondary efficacy endpoint DOR, including the investigator assessed results as per RECIST v1.1, is analyzed based on FAS and PPS. DoR will only be assessed in subjects whose BoR is PR or CR. The end date of tumor response must be consistent with the PD date of PFS or the date of death, and the Kaplan-Meier product-limit method will be used to calculate the median survival time of each treatment group and estimate the corresponding 95% CIs. The analysis is carried out using methods similar to those for the primary efficacy endpoint.
- Based on FAS, PPS, and evaluable patients, the ORR and DCR in the two groups are calculated and their 95% CIs are calculated using the Clopper-Pearson method. The difference of rates between groups are calculated and its 95% CIs are calculated using the Wald (normal approximation) method. The P values are calculated by the stratified Cochran–Mantel–Haenszel (CMH) (primary analysis) and the unstratified Pearson chi-square tests. Confirmed and unconfirmed CR/PR are analyzed, respectively.
- Based on FAS, PPS, and evaluable patients, the percentage of patients with SD for  $\geq 6$  weeks are calculated, and their 95% CIs are calculated using the Clopper-Pearson method. The difference between groups and its 95% CI are calculated using the Wald (normal approximation) method. The P values are calculated by the stratified CMH and the unstratified Pearson chi-square tests.

- Based on FAS and PPS, the 6- and 12-month OS rates, the Kaplan-Meier method is used to estimate rates and corresponding 95% CIs of the two groups are calculated using the log-log transformation according to the normal approximation with back transformation to CIs on the untransformed scale.

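### The protocol defines the PFS rates, ORR, DCR and SD rate on subjects who reach week 8, against its own Section 12.3 and the SAP; under the SAP the resulting inflation is confined to the additional evaluable-set analysis

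*Protocol*

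**What the plan says.** **Protocol definitions.** Protocol 2.3 describes the 3-, 6- and 12-month PFS rates as "Defined as the proportions of evaluable patients without disease progression from the start of the trial to 3, 6, and 12 months". ORR is "Defined as the proportion of evaluable subjects who have a tumor response assessed by RESIST 1.1" and DCR is "Defined as the proportion of evaluable subjects who have disease control assessed by RESIST 1.1". The SD rate is also a percentage of evaluable patients. The set is fixed in the same section: "Evaluable subjects are defined as all subjects who have received at least 2 cycles (8 weeks) of apatinib treatment", with a tumour evaluation after those 8 weeks. Protocol 10.2 repeats the evaluable denominator for the PFS rates, DCR and SD rate; its ORR text speaks only of patients.

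**Protocol analysis section.** Protocol 12.3 says that all efficacy endpoints are analysed on the FAS and the PPS. It does not mention the evaluable set.

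**SAP.** Section 6.1 makes the FAS the primary set for efficacy. Section 3.2 defines ORR and DCR as proportions of subjects, without restricting them to evaluable ones. Section 7.3.2 reads "Based on FAS and PPS, the 3-, 6-, and 12-month PFS rates, the Kaplan-Meier method was used to estimate rates", and it computes ORR, DCR and SD rate on the FAS, the PPS and evaluable patients. Section 6.3 introduces the evaluable analysis as an addition and uses the protocol's definition of the set.

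**A contrast within the SAP.** The PPS also needs a minimum of treatment (1 cycle), but SAP 6.2 carves out early progressors: "except for those with clear medical evidence of PD". The evaluable set has no such exception, for progression or for death.

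**The concern.** Membership of the evaluable set depends on what happens after randomisation. A subject who dies in week 5, or stops for toxicity in cycle 1, is a treatment failure, yet under the protocol definitions that subject is not counted at all. Removing failures from the denominator while the numerator stays the same can only raise the rate. The share removed need not be equal in the two arms, so a comparison within the set is no longer a randomised one.

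The PFS-rate wording has a further gap. It counts patients free of progression and says nothing of death, although PFS in the same section ends at progression or death. Read literally, a death without documented progression is a success.

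The protocol's RECIST appendix (Appendix 1, Section 2.7) says that the conditions for early progression, early death and non-evaluability should be described in each protocol. Neither document says how early death or early progression counts towards ORR or DCR.

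At stake is which of several rates per endpoint is the defined one, and how far the evaluable-set figures can be trusted.

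**Working it through.** **1. Which denominator applies where**

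| Endpoint | Protocol 2.3 | Protocol 10.2 | Protocol 12.3 | SAP 7.3.2 |
|---|---|---|---|---|
| PFS rates | evaluable | evaluable | FAS, PPS | FAS, PPS (Kaplan-Meier) |
| ORR | evaluable | patients | FAS, PPS | FAS, PPS, evaluable |
| DCR | evaluable | evaluable | FAS, PPS | FAS, PPS, evaluable |
| SD rate | evaluable | evaluable | FAS, PPS | FAS, PPS, evaluable |

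The protocol disagrees with itself on every row except ORR in 10.2, where no set is named. The SAP agrees with Protocol 12.3 and adds the evaluable set for three endpoints.

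**2. The plan's own figure**

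The documents give no figure for the size of the evaluable set. The OS medians used below (6 months placebo, 8.5 months apatinib; Protocol 4.3) do reproduce the stated total of 331:

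- HR = 6/8.5 = 0.706.
- Events (Schoenfeld, 2:1, two-sided 0.05, 80% power) = (1.960 + 0.842)² / [(2/9)(ln 0.706)²] = 291.1, so 292.
- Event probability with exponential survival, 12 months' accrual and 36 months in total: 0.893 if the 15% loss is spread over 36 months, 0.876 if over 24.
- N = 291.1/0.893 = 326, or 291.1/0.876 = 332.

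**3. Deaths before week 8**

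56 days = 56/30.4375 = 1.84 months. With exponential survival, S = 2^(−1.84/median).

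| Arm | S at 8 weeks | Dead | At N = 390 (2:1) | Inflation 1/S |
|---|---|---|---|---|
| Apatinib | 2^(−1.84/8.5) = 0.861 | 13.9% | 36 of 260 | 1.16 |
| Placebo | 2^(−1.84/6) = 0.809 | 19.1% | 25 of 130 | 1.24 |

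For deaths this is an upper illustration. Inclusion criterion 8 requires an expected survival of at least 12 weeks, so early deaths should be fewer than a constant hazard implies. Early stops for toxicity or progression would add to the number removed.

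**4. Effect on a reported rate**

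Rate in the evaluable set = FAS rate / (1 − share removed), when everyone removed is a failure. Take the phase II FAS DCR of 37.3% at 750 mg (Protocol 1.5.7):

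- 13.9% removed: 37.3/0.861 = 43.3%.
- Assumed shares of 5%, 10%, 20% and 30%: 39.3%, 41.4%, 46.6% and 53.3%.

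**5. Direction between arms**

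Suppose the true DCR were 30% in both arms. This is an assumption; 30% is also the supportive-care figure used to design the phase II trial (Protocol 1.5.7). Removing deaths alone gives 30/0.861 = 34.9% on apatinib and 30/0.809 = 37.1% on placebo. On this component the placebo rate gains more. Toxicity stops would push the other way if they are commoner on apatinib.

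**6. The treatment named in the definition**

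Both Protocol 2.3 and SAP 6.3 require 8 weeks of apatinib. Read literally, no placebo subject can be evaluable.

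**The case against.** The strongest reply is that the SAP already settles the planned analysis. The FAS is primary, the PFS rates are Kaplan-Meier on the FAS and PPS, and ORR, DCR and SD rate are all computed on the FAS. Most of this stands. A reader of Protocol 2.3 alone might infer that early failures disappear from the trial's main PFS rates, ORR and DCR; Protocol 12.3 and SAP 6.1 and 7.3.2 do not support that. What survives is the conflict between the protocol's definitions and those sections, and an evaluable-set analysis that SAP 7.3.2 lists beside the FAS and PPS with P values. The primary-analysis label there attaches to the stratified CMH test and not to a set.

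Second, early progression is rarely lost. "The first efficacy evaluation is carried out at the end of Cycle 2" (Protocol, Schedule of Activities notes), so progression first seen on that scan after two full cycles stays in. This is right for most subjects. However, Protocol 4.6 allows a window of 7 days either side and stops treatment at imaging-confirmed progression. A subject with progression on a day-50 scan has not had 8 weeks of drug and drops out; one with stable disease that day continues and can qualify.

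Third, counting a death as a PFS success is a very literal reading. It is: PFS itself includes death in Protocol 2.3 and 10.2, and SAP 7.1.3 treats death as an event. No analysis in the SAP counts death as success. The wording still needs repair.

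Fourth, a reader might add the early adverse-event withdrawals from phase II (3 of 51 at 750 mg; Protocol 4.5.2 and 1.5.7) and reach 37.3/(1 − 0.139 − 0.059) = 46.5%. That assumes that no one who stopped early also died before week 8, and it makes no matching deduction on placebo. The documents support neither step.

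**Conclusion.** The protocol's definitions of the PFS rates, ORR, DCR and SD rate conflict with Protocol 12.3 and with the SAP, and the evaluable set they rest on removes early failures without exception. If the SAP is followed, only the additional evaluable-set analysis of ORR, DCR and SD is distorted.

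On deaths alone the inflation is about 1.16-fold on apatinib and 1.24-fold on placebo. This rests on the plan's OS medians, exponential survival from day 0, and every early death being a failure in the FAS. The life-expectancy criterion makes these upper figures for deaths; early stops, which the documents do not let us size for this trial, would add to them.

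It is tempting to conclude that the evaluable set favours apatinib. The documents do not show that. Both arms are inflated, deaths alone raise placebo more, and the net direction depends on exclusions per arm that are not given.

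These are secondary endpoints. The OS analysis, the sample size and the FAS analyses are unaffected.

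**What to change.** 1. **Protocol 2.3 and 10.2.** Define the PFS rates as Kaplan-Meier estimates in the FAS with death as an event. Make the FAS the denominator for ORR, DCR and SD rate, and count subjects without a post-baseline tumour evaluation as non-responders. Set and estimator then match SAP 7.3.2; the non-responder rule is not written there and should be added. Protocol 12.3 lists a CMH test for the PFS rates, which should be brought into line.
2. **SAP 6.3 and Protocol 2.3.** Label the evaluable-set analysis supplementary. Include in that set, as non-responders, all treated subjects who die, progress or stop for toxicity before the week-8 evaluation.
3. **The same definition in both documents.** Refer to study drug instead of apatinib, so that placebo subjects can qualify.

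The cost is wording, plus slightly less favourable evaluable-set rates. No new data, subjects or follow-up are needed.
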